Specific Aim 1: *To determine the efficacy of ION vs. placebo in reducing meth use, as determined by the proportion of meth-positive urine tests.* As in our prior trial, a GEE Poisson model with robust standard errors will be used to compare weekly urine test results by treatment assignment; this provides easier-to-interpret risk-ratios²¹⁸ rather than odds-ratios. The treatment effect of ION vs. placebo will be modeled as linearly increasing and summarized by the between-group difference in means at 12 weeks, net of any baseline difference. *Minimum Detectable Effects (MDEs) with sample size:* Based on the prior trial (93% retention with an 8-week follow-up), we estimate that 80% of participants will be retained at 12 weeks, and within-subject correlation will be 0.45. Under these assumptions, the study sample will have 80% power in 2-sided tests with a type-I error rate of 5% to detect net between-group differences in the reduction in sweat patch positivity of ~14.5 percentage points. In the Project iN study, we have observed reductions on meth use between 18%-22% among the ION arm, compared to placebo, in ITT and sub-group analyses.¹⁰⁹ Therefore, we believe that the reductions in meth use we are powered to detect in this aim are reasonable to anticipate. *In sensitivity analyses*, we will also evaluate between-group differences on changes in: 1) any meth-positive samples or self-report of meth use in timeline follow back; and 2) meth positivity from self-report only. Concordance of the urine testing, and self-reported measures will be examined using weighted Kappa and correlations. We recognize that meth use is a stigmatized behavior that may be underreported. Hence, in the event of discrepancies between urine results and timeline follow back data on meth use, we will treat the urine test results as the gold standard. *Additionally, we will analyze participant's perception of whether the EMI prompts had effects on various HBM constructs and explore whether these moderate treatment effects on meth use.*^{119,120}

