Specific Aim 2: *To determine the efficacy of ION vs. placebo in reducing meth-associated sexual risk behaviors.* We will use GEE Poisson models with robust standard errors to assess evidence that the intervention reduces HIV risk behaviors, including number of sex partners, number of sex partners with whom meth is used and episodes of condomless sex with serodiscordant partners. *MDEs:* Using data from our prior trial on baseline means, within-subject correlation, and over-dispersion, we estimate that the study sample of 60 participants will have 80% power to detect ~46% net reductions in the numbers of sexual partners, ~67% reductions in partners with whom meth is used, and ~52% reductions in episodes of condomless sex with serodiscordant partners at 12 weeks. In our Project iN study, we have observed statistically significant reductions on sexual risk outcomes ranging between 85%-89% among the treatment arm, compared to placebo.¹⁰⁹ Therefore, given the results from the prior trial, we believe that the reductions we are powered to detect in this aim are reasonable to anticipate. *In sensitivity analyses*, we will examine how PrEP use and viral suppression status of participants and their partners (partner data assessed via self-reported egocentric data collection from participants)²¹⁹ modify treatment effects on sexual risk behaviors. We will also examine whether there is evidence of effect modification depending on whether both the study participant and partner, the

participant only, the partner only, or neither the participant nor the partner used a biomedical HIV prevention tool (PrEP or ART).²¹⁹

Specific Aim 3: *To determine the efficacy of ION vs. placebo in increasing PrEP adherence among HIV-negative participants and ART adherence among participants living with HIV, as measured by serum drug-levels and viral suppression rates.* We will use GEE Poisson models with robust standard errors to assess evidence that the intervention increases PrEP and ART adherence. *MDEs:* Using the assumptions for loss to follow-up from Project iN for Aim 1, we estimate that the study sample of 60 participants will have 80% power to detect 10-19 percentage point increases in PrEP/ART adherence, depending on within-subject correlations and adherence levels in the reference group.^{126,220}

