11.0 Sample Size and Eligibility Criteria

11.1 ENROLLMENT TARGET: How many people will you enroll:

60

If there are multiple participant groups, indicate how many people will be in each group:

The ION+EMI study will enroll 60 participants in the double-blinded placebo controlled clinical trial where 40 participants will receive Intermittent Oral Naltrexone and 20 participants will receive placebo.

11.3 SAMPLE SIZE JUSTIFICATION: Explain how and why the number of people was chosen. For multi-site studies, this is referring to the number that will be enrolled across all sites:

For the phase 2b clinical trial, a sample size of 60 was selected to provide 80% power in 2-sided tests with a type-I error rate of 5% to detect between a 18-22% reduction of meth use among the ION arm, compared to placebo, in ITT and sub-group analyses. We hypothesized on pharmacologic grounds that oral naltrexone will reach full efficacy against meth use almost immediately; accordingly we expect treatment-control differences to be approximately constant over the 12 weeks of the trial. Based on the prior trial (93% retention), we estimate that 90% of participants will be retained at 12 weeks. Under these assumptions, the minimum detectable effects for our outcomes are calculated as follows:

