Specific Aim 1: *To determine the efficacy of ION vs. placebo in reducing meth use, as determined by the proportion of meth-positive sweat patch tests.* As in our prior trial, a GEE Poisson model with robust standard errors will be used to compare weekly urine test results by treatment assignment; this provides easier-to-interpret risk-ratios²¹⁸ rather than odds-ratios. The treatment effect of ION vs. placebo will be modeled as linearly increasing and summarized by the between-group difference in means at 12 weeks, net of any baseline difference. *Minimum Detectable Effects (MDEs) with sample size:* Based on the prior trial (93% retention with an 8-week follow-up), we estimate that 90% of participants will be retained at 12 weeks, and within-subject correlation will be 0.45. Under these assumptions, the study sample of 60 participants will have 80% power in 2-sided tests with a type-I error rate of 5% to detect net between-group differences in the reduction in urine positivity of ~24 percentage points, equivalent to a relative rate reduction of 32%. We have observed similar reductions on meth use in ITT and sub-group analyses in prior trials.¹⁰⁹ Therefore, we believe that the reductions in meth use we are powered to detect in this aim are reasonable to anticipate. *In sensitivity analyses,* we will also evaluate between-group differences on changes in: 1) any meth-positive samples or self-report of meth use in timeline follow back; and 2) meth positivity from self-report only. Concordance of the urine testing, and self-reported measures will be examined using weighted Kappa and correlations. We recognize that meth use is a stigmatized behavior that may be underreported. Hence, in the event of discrepancies between urine test results and timeline follow back data on meth use, we will treat the urine test results as the gold standard. *Additionally, we will analyze participant's perception of whether the EMI prompts had effects on various HBM constructs and explore whether these moderate treatment effects on meth use.*^{119,120}

Specific Aim 2: *To determine the efficacy of ION vs. placebo in reducing meth-associated sexual risk behaviors.* We will use GEE Poisson models with robust standard errors to assess evidence that the intervention reduces HIV risk behaviors, including number of sex partners,

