number of sex partners with whom meth is used and episodes of condomless sex with serodiscordant partners. *MDEs:* Using data from our prior trial on baseline means, within-subject correlation, and over-dispersion, we estimate that the study sample of 60 participants will have 80% power to detect ~46% net reductions in the numbers of sexual partners. In our Project iN study, we have observed statistically significant reductions on sexual risk outcomes ranging between 85%-89% among the treatment arm, compared to placebo.¹⁰⁹ Therefore, given the results from the prior trial, we believe that the reductions we are powered to detect in this aim are reasonable to anticipate. *In sensitivity analyses*, we will examine how PrEP use and viral suppression status of participants and their partners (partner data assessed via self-reported egocentric data collection from participants)²¹² modify treatment effects on sexual risk behaviors. We will also examine whether there is evidence of effect modification depending on whether both the study participant and partner, the participant only, the partner only, or neither the participant nor the partner used a biomedical HIV prevention tool (PrEP or ART).²¹²

Specific Aim 3: To determine the efficacy of ION vs. placebo in increasing PrEP adherence among HIV-negative participants and ART adherence among participants living with HIV, as measured by serum drug-levels and viral suppression rates. We will use GEE Poisson models with robust standard errors to assess evidence that the intervention increases PrEP and ART adherence. *MDEs:* Using the assumptions for loss to follow-up from Project iN for Aim 1, we estimate that the study sample with 60 participants will have 80% power to detect 10-19 percentage point increases in PrEP/ART adherence, depending on within-subject correlations and adherence levels in the reference group.^{126,220}

The sample size of 60 participants is the minimum number required to have sufficient power to determine the MDEs of intermittent naltrexone in reducing meth use for the phase 2b study.

11.4 * PARTICIPANT AGE RANGE: Eligible age ranges: (REQUIRED)

- 0-6 years
- 7-12 years
- 13-17 years
- 18-64 years
- 65+

11.5 * STUDY POPULATIONS: Data will be collected from or about the following types of people (check all that apply): (REQUIRED)

- Inpatients
- Outpatients
- Family members or caregivers
- Providers
- People who have a condition but who are not being seen as patients
- Healthy volunteers

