**07/13/2021**

## Statistical Analyses

We will use generalized estimating equations (GEE) to estimate treatment effects on repeated study outcomes. Primary analyses will be by intention-to-treat (ITT). In prior trials, we had excellent visit retention and study completion. Nonetheless, in this high-risk population, missing data may be encountered. We will conduct sensitivity analyses imputing all missing urine samples as positive, adjusting for baseline correlates of missingness, and using inverse probability of censoring weights.

**Specific Aim 1:** *To determine the efficacy of ION vs. placebo in reducing meth use, as determined by the proportion of meth-positive urine tests.* As in our prior trial, a GEE Poisson model with robust standard errors will be used to compare weekly urine test results by treatment assignment; this provides easier-to-interpret risk ratios rather than odds ratios. The treatment effect of ION vs. placebo will be modeled as linearly increasing and summarized by the between-group difference in means at 12 weeks, net of any baseline difference.

**Minimum Detectable Effects (MDEs) with sample size:** Based on the prior trial (93% retention), we estimate that 90% of participants will be retained at 12 weeks, and within-subject correlation will be 0.45. Under these assumptions, the study sample of 54 participants will have 80% power in 2-sided tests with a type-I error rate of 5% to detect net between-group differences in the reduction in urine positivity of ~24 percentage points, equivalent to a relative rate reduction of 32%. We have observed similar reductions on meth use in ITT and subgroup analyses in prior trials. Therefore, we believe that the reductions in meth use we are powered to detect in this aim are reasonable to anticipate.

**Specific Aim 2:** *To determine the efficacy of ION vs. placebo in reducing meth-associated sexual risk behaviors.* We will use GEE Poisson models with robust standard errors to assess evidence that the intervention reduces HIV risk behaviors, including number of sex partners, and number of sex partners with whom meth is used.

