**MDEs:** Using data from our prior trial on baseline means, within-subject correlation, and over-dispersion, we estimate that the study sample of 54 participants will have 80% power to detect ~46% net reductions in the numbers of sexual partners and ~67% reductions in partners with whom meth is used. In our Project iN study, we have observed statistically significant reductions on sexual risk outcomes ranging between 85%-89% among the treatment arm, compared to placebo. Therefore, given the results from the prior trial, we believe that the reductions we are powered to detect in this aim are reasonable to anticipate.

**Specific Aim 3:** *To determine the efficacy of ION vs. placebo in increasing PrEP adherence among HIV-negative participants and ART adherence among participants living with HIV, as measured by serum drug levels and viral suppression rates.* We will use GEE Poisson models with robust standard errors to assess evidence that the intervention increases PrEP and ART adherence.

**MDEs:** Using the assumptions for loss to follow-up from Project iN for Aim 1, and informed by the within subject correlations of a PrEP adherence measure in the EPIC study and of detectable viral loads among HIV+ participants in a Mirtazapine trial for MSM who use meth, we estimate that the study sample of 54 participants will have 80% power to detect 10-19 percentage point increases in PrEP/ART adherence, depending on within-subject correlations and adherence levels in the reference group.

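### Retention at 12 weeks is 80% in section 8.13 but 90% in section 11.3 and the SAP, yet the Aim 2 partner-number and Aim 3 adherence detectable effects are the same in all three and cannot be traced to one stated n.

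*Protocol*

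**What the plan says.** **Retention.** In Protocol 8.13 (Statistical Methods, Aim 1): "we estimate that 80% of participants will be retained at 12 weeks". In Protocol 11.3 (Sample Size Justification, Aim 1): "we estimate that 90% of participants will be retained at 12 weeks, and within-subject correlation will be 0.45". In the SAP (Statistical Analyses, Aim 1): "Based on the prior trial (93% retention), we estimate that 90% of participants will be retained at 12 weeks". All three start from 93% in the pilot trial.

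**Sample.** Protocol 11.1 states that "The ION+EMI study will enroll 60 participants in the double-blinded placebo controlled clinical trial", split 40 to naltrexone and 20 to placebo. Section 11.3 closes with "The sample size of 60 participants is the minimum number required to have sufficient power". The SAP attaches its power statements to 54 participants and does not define that number.

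**Aim 2.** Protocol 8.13: "the study sample of 60 participants will have 80% power to detect ~46% net reductions in the numbers of sexual partners". SAP: "the study sample of 54 participants will have 80% power to detect ~46% net reductions in the numbers of sexual partners". Section 11.3 repeats ~46% with 60 participants. The ~67% figure (partners with whom meth is used) is in 8.13 and the SAP only, and ~52% (condomless serodiscordant sex) is in 8.13 only. The stated inputs are the prior trial's baseline means, within-subject correlation and over-dispersion; no retention rate is named.

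**Aim 3.** All three texts give 10-19 percentage points at 80% power and say that the loss to follow-up is the one assumed for Aim 1. The range is said to depend on within-subject correlation and on adherence in the reference group.

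**The concern.** A detectable effect at fixed power depends on how much follow-up is observed. Here the assumed loss doubles, from 10% to 20%, between two sections of one protocol with the same enrolment, while the effects stay the same. For Aim 3 the link is explicit, because its loss to follow-up is taken from the very assumption that differs. The unlabelled 54 in the SAP adds a second ambiguity.

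At stake is whether a reader can tell what this trial is powered to detect for two of its three aims. If the effects belong to 90% retention, 8.13 overstates power. If they belong to 80%, 11.3 understates it.

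**Working it through.** **1. Can the stated effects be reproduced?** No. The baseline means, over-dispersion, correlations, reference adherence and PrEP/ART subgroup sizes are not given. What can be checked is whether the three statements agree with one another.

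**2. Numbers retained.**
- 8.13: 60 × 0.80 = 48
- 11.3: 60 × 0.90 = 54
- SAP, if 54 is retained: 54
- SAP, if 54 is enrolled: 54 × 0.90 = 48.6

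If 54 means retained, the SAP agrees with 11.3 and not with 8.13. If it means enrolled, the SAP nearly agrees with 8.13 (48.6 against 48) and not with 11.3. Neither reading fits all three, because 8.13 and 11.3 both start from 60.

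**3. Size, counting completers only.** The detectable effect scales with 1/√n, on the log rate ratio for Aim 2 and on the risk difference for Aim 3. At 80% power and two-sided 5%, the standardised effect is 1.960 + 0.842 = 2.802.

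Suppose the figures are right at 54 retained. At 48 the factor is √(54/48) = 1.061.
- Aim 2: 1 − exp(1.061 × ln 0.54) = 48.0%, in place of 46%
- Aim 3: 10 × 1.061 = 10.6 and 19 × 1.061 = 20.2 points, in place of 10-19
- Power at the stated effects: Φ(2.802/1.061 − 1.960) = 75.2%

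Suppose instead that they are right at 48. At 54 the factor is 0.943, giving 44.1%, 9.4-17.9 points, and 84.4% power at the stated effects.

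**4. Size, keeping dropouts' partial follow-up.** GEE uses the visits made before dropout. I took N = 60, 2:1 allocation, baseline plus months 1 to 3 (the Table 4 schedule for these outcomes), dropout spread evenly over time, exchangeable correlation of 0.2 to 0.7 (assumed, since none is given for Aims 2 and 3), and the generalised least squares variance of the treatment effect. The ratio of standard errors, 80% against 90% retention, replaces 1.061:

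| Treatment effect over time | SE ratio | Aim 2 | Aim 3 (points) | Power at stated effects |
|---|---|---|---|---|
| Linear to week 12 | 1.036-1.045 | 47.2-47.5% | 10.4-10.5 to 19.7-19.9 | 76.5-77.2% |
| Constant | 1.014-1.022 | 46.5-46.7% | 10.1-10.2 to 19.3-19.4 | 78.3-78.9% |

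Both shapes are shown because 8.13, 11.3 and the SAP model the Aim 1 effect as linearly increasing, while the opening of 11.3 expects it to be roughly constant.

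**5. Cross-check on Aim 1.** A difference of ~24 points equal to a 32% relative reduction implies a reference positivity of 0.24/0.32 = 75%. With weekly tests, correlation 0.45 and a linear effect, the method of step 4 gives 24.0 points for 54 enrolled at 90%, 22.7 for 60 at 90%, 23.7 for 60 at 80%, and 23.1 for 54 with complete data. The closest match is 54 enrolled, but this is not the sponsor's own calculation and does not settle what 54 means.

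Section 8.13 gives ~14.5 points of sweat-patch positivity with the lower retention, against ~24 points of urine positivity in 11.3 and the SAP. Lower retention raises a detectable effect, so retention cannot explain the smaller figure.

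**The case against.** The strongest defence is that nothing has been shown to be miscalculated. Aim 2 names no retention input, its figures are marked approximate, and Aim 3 is a range resting on unstated correlations and reference adherence. With partial follow-up kept and a constant effect, the shift is close to rounding. This stands in part. A reader might infer that a particular Aim 2 or Aim 3 power statement is proven false, and the documents do not support that, because none of these effects can be rebuilt from what is printed.

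A reader might also take 60 and 54 as a contradiction in themselves. They are not: 60 × 0.90 = 54, and on that reading 60 can still be the minimum to enrol. Nor are all the Aim 2 effects repeated three times; only ~46% is.

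It may also seem that 80% is simply the slip and 90% the truth. Two things favour 90%: 0.93^(12/8) = 0.897, and the team's completed 12-week trials in Table 1 retained 83-95%. But the extrapolation assumes a constant dropout rate, section 8.5 reports the pilot as 95% retention and 93% completion, and one of those trials retained 83%, so 80% could be deliberate caution.

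None of this removes the conflict between 80% and 90% at the same N, with Aim 3 tied to it.

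**Conclusion.** The point holds as an inconsistency of inputs with untraceable outputs. The retention assumption is wrong in at least one of the three places, and the repeated ~46% and 10-19 points were either not recalculated or cannot be tied to a stated n. The consequence is modest. If the effects are correct at 90% retention, then at 80% power falls by about 5 percentage points counting completers only, and by roughly 1 to 3.5 points when partial follow-up is used. The detectable effects move by at most about 2 points on 46% and about 1 point on 19.

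These sizes assume 1/√n scaling, equal dropout in the two arms and, for the smaller range, evenly spread dropout with correlation between 0.2 and 0.7. The finding bears on the stated power for Aims 2 and 3; it does not change the planned enrolment or the analysis method.

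**What to change.** 1. Use one 12-week retention rate in 8.13, 11.3 and the SAP. The Table 1 experience is consistent with 90%, but the sponsor must confirm the rate.
2. In the SAP, say whether 54 is enrolled or retained, and print it beside 60 randomised 40:20. The sponsor should establish this before the text is changed.
3. For each Aim 2 and Aim 3 detectable effect, state the n and retention used, with the baseline mean, over-dispersion, correlation or reference adherence behind it.
4. Rerun the calculation and restate any effect that changes. Reconcile the Aim 1 effects (~14.5 points of sweat-patch positivity, ~24 points of urine positivity) in the same rerun.

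The cost is wording in two documents and a rerun of an existing calculation. No extra participants or procedures are needed. The downside is that some stated detectable effects may become slightly less favourable.

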9.0 Biospecimen Collection and/or Bank Administration

9.1 * TYPE OF SPECIMENS (check all that apply): (REQUIRED)

- Blood (provide amount below)
- Tissue (describe below)
- Other type of biospecimen, such as sputum, cerebrospinal fluid, buccal swabs, etc. (describe below)
- Existing/archival materials (name source below)

Briefly describe the types of biospecimens that will be collected. Provide the amount of blood, if applicable. For leftover/existing/archival material, identify the source:

Urine samples will be collected for methamphetamine and other substance use metabolites. Sweat patches will be collected for methamphetamine, methamphetamine metabolites and other substance use metabolites. Among HIV-negative participants on PrEP and HIV-positive participants on ART, we will test for drug level concentration and RNA viral load from 5 ml. blood samples.

9.3 * SPECIMENS ARE: (check all that apply): (REQUIRED)

- Leftover specimens from a clinical diagnostic or therapeutic procedure
- Specimens collected for research purposes only (including extra samples taken during a clinical procedure)
- Other

9.4 * FUTURE SPECIMEN USE: Will any specimens or portions of specimens be retained after the study is over for possible use in future research studies: (REQUIRED)

Yes No

9.6 * SPECIMEN DESTINATION: Indicate where specimens will ultimately be stored: (REQUIRED)

Outside Entities: Indicate where specimens will be sent if they will not remain at UCSF (choose at least one; check all that apply):

Cooperative group bank
 NIH
 Other university or collaborator
 Industry sponsor
 Other
 N/A - all specimens will remain at UCSF

Specify to what institution, cooperative group, or company specimens will be transferred:

San Francisco Department of Public Health

Internal Storage: If specimens will remain at UCSF, in what kind of facility will they reside (choose at least one; check all that apply):

UCSF repository/bank being established under this protocol
 Existing UCSF specimen repository/bank with IRB approval
 National cooperative group bank housed at UCSF
 Other location at UCSF (please describe)
 N/A - no specimens will be retained at UCSF facilities

9.7 SPECIMENS SENT OUTSIDE UCSF - IDENTIFIABILITY: Will direct identifiers be associated with specimens or shared with other researchers and/or outside entities:

Yes
 No
 N/A - Specimens will not be shared with others

